13.3 Appendix 3 World Allergy Organization Grading System

World Allergy Organization subcutaneous immunotherapy systemic reaction grading system

Grade 1	Grade 2	Grade 3	Grade 4	Grade 5
Symptom(s)/sign(s) of 1 organ system present	Symptom(s)/sign(s) of more than 1 organ system present	Lower respiratory	Lower or upper respiratory	Death
Cutaneous	Lower respiratory	Asthma (eg, 40% PEF or FEV1 drop	Respiratory failure with or without loss of consciousness	
Generalized pruritus, urticaria, flushing, or sensation of heat or warmth	or Asthma: cough, wheezing, shortness of breath (eg, less than 40% PEF or FEV1 drop, responding to an inhaled bronchodilator)	or NOT responding to an inhaled bronchodilator)	or without loss of consciousness	
or		Upper respiratory	Cardiovascular	
Angioedema (not laryngeal, tongue or uvular)	responding to an inhaled bronchodilator)	Laryngeal, uvula, or tongue edema with or without stridor	Hypotension with or without loss of consciousness	
or	or			
Upper respiratory	Gastrointestinal			
Rhinitis - (eg, sneezing, rhinorrhea, nasal pruritus and/ or nasal congestion)	Abdominal cramps, vomiting, or diarrhea			
or	or			
Throat-clearing (itchy throat)	Other			
or	Uterine cramps			
Cough perceived to originate in the upper airway, not the lung, larynx, or trachea				
or				
Conjunctival				
Erythema, pruritus or tearing				
Other				
Nausea, metallic taste, or headache				

[figure not shown]
Source: Cox 2010

13.4 Appendix 4 Blood log

Sample	Sample type	Visit																		
		206*	301	302	303	304	305	306	307	308	309	310	311	312	313	401	402	403	404	405
		Day																		
		-21/-14	1	29	57	85	113	141	169	197	225	253	281	309	337	365	421	477	533	701
Chemistry	Serum 1.5mL	3.5	3.5	3.5	3.5	3.5	3.5	3.5	3.5	3.5	3.5	3.5	3.5	3.5	3.5	3.5	3.5	3.5	3.5	3.5
Haem+ PT(INR)	Blood 4.5+2mL	6.5	6.5	6.5	6.5	6.5	6.5	6.5	6.5	6.5	6.5	6.5	6.5	6.5	6.5	6.5	6.5	6.5	6.5	6.5
Total blood volume for labs/ [redacted] per visit		16.1	10	10	10	10	10	10	10	10	10	10	10	10	10	10	10	10	10	10

Sample	Sample type	Visit																		
		206*	301	302	303	304	305	306	307	308	309	310	311	312	313	401	402	403	404	405
		Day																		
		-21/-14	1	29	57	85	113	141	169	197	225	253	281	309	337	365	421	477	533	701
Total blood Volume/visit		26.1	10	10	10	10	10	10	20	10	10	10	10	10	20	10	16	10	16	20
Total blood volume from Visit 301 - 405		222 mL																		
*: Blood volume from assessments done as a part of Visit 206 not included in Total blood volume for this extension study																				

13.5 Appendix 5 ePRO tools

Samples of questionnaire provided here are for illustrative purposes only. The text format and wording might slightly vary.

Patient Diary: Urticaria Patient Daily Diary (UPDD)

General Instructions

Please answer each question to the best of your ability.

There are no right or wrong answers.

For each question, please choose the response that describes your experience.

Please pay close attention to the timeframe of interest. Some questions ask about the past 12 hours, while others ask about the past 24 hours.

Instructions for Counting the Number of Hives

Count each hive separately even if you have more than one hive grouped together with other hives.

Today's Date

day		month		year					

Please complete this section every morning throughout the duration of the study.
(Please circle only one response.)

1. Thinking about the past 12 hours, please record the severity of itch and the number of hives you may have had associated with your skin condition. Please count each hive separately even if you have more than one hive grouped together with other hives.

Itch (severity)

- 0 = none
- 1 = mild
- 2 = moderate
- 3 = severe

Hives (number)

- 0 = none
- 1 = between 1 and 6 hives
- 2 = between 7 and 12 hives
- 3 = greater than 12 hives

Today's Date

day	month	year					

Please complete this section every evening throughout the duration of the study.
(Please circle only one response.)

2. Thinking about the past 12 hours, please record the severity of itch and the number of hives you may have had associated with your skin condition. Please count each hive separately even if you have more than one hive grouped together with other hives.

Itch (severity)

- 0 = none
- 1 = mild
- 2 = moderate
- 3 = severe

Hives (number)

- 0 = none
- 1 = between 1 and 6 hives
- 2 = between 7 and 12 hives
- 3 = greater than 12 hives

Today's Date

day	month	year					

Please complete this section once each day throughout the duration of the study
(preferably at the same time each day).

[figure not shown]
(Please circle only one response.)

3. Please rate how much your hives or itch interfered with your sleep during the past 24 hours.

- 0 = No interference
- 1 = Mild, little interference with sleep
- 2 = Moderate, awoke occasionally, some interference with sleep
- 3 = Substantial, woke up often, severe interference with sleep

4. Please rate how much your hives or itch interfered with your daily activities during the past 24 hours. This could include work, school, sports, hobbies, and activities with friends and family.

- 0 = No interference
- 1 = Mild, little interference with daily activities
- 2 = Moderate, some interference with daily activities
- 3 = Substantial, severe interference with daily activities

These next questions are about your symptoms and how you managed them during the past 24 hours.

5. During the **past 24 hours**, how many tablets of rescue medication did you use in order to control symptoms of your skin condition such as itch or hives?

The maximum number of tablets per day should be according to your doctor's recommendation.

- 6a. During the **past 24 hours**, did you have any rapid swelling on your face, (especially your eyelids or lips), inside your mouth (including your throat or tongue), or elsewhere on your body? This rapid swelling, also called angioedema, is at a deeper level under your skin than hives.

0 = No (GO TO Question 7)

1 = Yes

- 6b. If Yes, how did you treat this rapid swelling? (Circle all that apply.)

0 = Did nothing (GO TO Question 7)

1 = Took some prescription or non-prescription medication

2 = Called my doctor, nurse or nurse practitioner

3 = Went to see my doctor, nurse or nurse practitioner

4 = Went to the emergency room at the hospital

5 = Was hospitalized

7. During the **past 24 hours**, did you or someone else call your doctor, nurse or nurse practitioner because of your skin condition?

0 = No

1 = Yes

This document covers statistical and analytical plans to evaluate long-term safety as well as efficacy outcome of QGE031 240 mg subcutaneous (s.c.) administered every 4 weeks (q4w) for 12 months in patients with chronic spontaneous urticaria (CSU) who completed the CQGE031C2201 study. This document does not cover statistical analysis on pharmacogenetic data analyses which will not be presented in the Clinical Study Report (CSR).

1.1 Study design

This study is a phase 2b open label, single arm, long-term safety extension for all patients who completed the core study CQGE031C2201 and fulfill the enrollment criteria for the extension study.

Approximately 240 subjects may enroll into this extension study. Enrollment criteria require subjects to complete the treatment epoch and at least visit 201 - 203 in the follow-up epoch in study CQGE031C2201 and present with active disease, as defined by weekly Urticaria Activity Score (UAS7) ≥ 12 .

The study consists of two epochs: open-label treatment and post-treatment follow up epoch. At or after visit 203, when the subjects become eligible to enroll in this extension study, they will complete all assessments associated with Visit 206 as a part of core study completion.

- Open-label treatment period: corresponds to 52 weeks, in which subjects are treated with QGE031 240 mg s.c. at 4-week intervals.
- Follow-up post-treatment period: in this follow-up epoch, the patients will be followed at 12-week intervals for 48 weeks.

As in the core study, patients will continue using their background medication i.e. H1-antihistamines (H1-AH) at approved or increased doses alone or in combination with H2-antihistamines (H2-AH) and/or a Leukotriene Receptor Antagonist (LTRA).

1.2 Study objectives and endpoints

1.2.1 Primary objective(s)

The primary objective of this study is to assess the long-term safety of QGE031 in adult CSU patients who completed the core study CQGE031C2201 using the following evaluations:

- Incidence and severity of non-serious and serious adverse events including any events of special interest;
- Changes in vital signs, laboratory assessments, and electrocardiograms (ECGs).

1.2.2 Secondary objectives

The secondary objective of this study is to assess the long-term efficacy of QGE031 in adult CSU patients who completed the CQGE031C2201 study by evaluation of:

- Sustained remission defined as maintaining $UAS7 \leq 6$ over 48 weeks post-treatment follow up epoch among the subjects achieving remission at the end of treatment epoch.

2 Statistical methods

The planned analysis is described in Section 9 (Data Analysis) of the study protocol which is available in Appendix 16.1.1 of the CSR.

2.1 Data analysis general information

Data will be analyzed [REDACTED] according to the data analysis Section 9 of the study protocol which is available in [\[Appendix 16.1.1\]](#) of the CSR. Important information is given in the following sections and details are provided, as applicable, in [\[Appendix 16.1.9\]](#) of the CSR.

2.1.1 Assessment windows

No assessment windows are defined for this study. Consequently, all by-visit summaries will be performed as per below scheduled visits.

Table 1-1 Assessment windows for scheduled visits

Analysis Visit	E1 Week	E1 Scheduled Day	Visit Window
E1 Baseline	Baseline	-21/-14, 1	Up to Day 1
E1 Week 4	4	29	NA
E1 Week 8	8	57	NA
E1 Week 12	12	85	NA
E1 Week 16	16	113	NA
E1 Week 20	20	141	NA

E1 Week 24	24	169	NA
E1 Week 28	28	197	NA
E1 Week 32	32	225	NA
E1 Week 36	36	253	NA
E1 Week 40	40	281	NA
E1 Week 44	44	309	NA
E1 Week 48	48	337	NA
E1 Week 52	52	365	NA
E1 Week 64	64	449	NA
E1 Week 76	76	533	NA
E1 Week 88	88	617	NA
E1 Week 100	100	701	NA

2.1.2 Definition of Study Day

The first day of administration of extension study treatment is defined as E1 Study Day 1 or Day 1.

All other study days will be labeled relative to Day 1. For event dates on or after Day 1, study day for a particular event date will be calculated as [Date of event] – [Date of first dose] + 1, i.e., Day 2, Day 3, etc., will be one day, two days, etc., after Day 1, respectively. For the dates before Day 1, study day for an event date will be calculated as [Date of event] – [Date of first dose], i.e., Day -1, Day -2, etc., will be one day, two days, etc., before Day 1, respectively. Duration of an event will be calculated as (Event end date – Event start date + 1).

The descriptor “Day 0” will not be used.

2.1.3 Definition of Study Week based on eDiary

A number of efficacy outcome measures (weekly itch severity score, weekly number of hives score, UAS7, [REDACTED]) are in the form of weekly scores derived from patient daily diary data. The extension study weeks are defined based on the study days (see Table 1-2), starting with Day 1, which is the day the patient receives the first extension study treatment. The extension study day for a particular diary date will be calculated as [Date of diary] – [Date of first extension study dose] + 1. Note that the baseline week is comprised of the 7 days prior to Day 1 (Day -7 to Day -1).

Table 1-2 Extension Study Week definition based on E1 Study Day

E1 Study Week	E1 Study Days
Baseline	(-7) - (-1)
1	1 - 7
2	8 - 14
w	$7 \times (w-1) + 1 - 7 \times w$

2.1.4 Baseline definitions

Core study baseline definition-

Core study baseline is the last assessment (including unscheduled visits) obtained before the first dose of core study treatment.

For the following demographic information - sex, race, ethnicity and height and baseline characteristics, randomization/background medication strata and positive chronic urticaria group, core study baseline information will be used.

Extension study baseline definition –

For eDiary weekly score, the E1 baseline is the score derived from E1 study day -7 to E1 study day -1.

If the questionnaire was completed more than once on the same date, on the last date on or before treatment start date, then the worst outcome (i.e. the highest score) of the duplicate observations on that date will be used for baseline.

For the safety analysis, the baseline will be the last assessment prior to or on the first study dose and on or after visit 206, unless otherwise specified. Note: if time is collected (i.e. hematology chemistry and ECG) the last assessment prior to or on the same time as first study dose will be used. If time is not collected then, the assessment is assumed to be prior if it's on the same date as first study dose.

2.1.5 Day of last dose of study treatment

The date of last dose will be collected via the case report form (CRF). The subject's exposure will be calculated using last dose + 28 days. If a subject discontinued early during the treatment period, then exposure will be calculated using last dose + 28 days, unless the patient dies, in which case the date of death will be used.

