5.2 Treatment arms

Patients will all be treated with QGE031 240 mg sc q 4 weeks for 52 weeks (13 treatments) in this open label study.

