5.6.2 Discontinuation of study treatment

Patients may voluntarily discontinue study treatment for any reason at any time.

The investigator should discontinue study treatment for a given patient if, on balance, he/she believes that continuation would be detrimental to the patient's well-being.

As in study CQGE031C2201E1, study treatment must be discontinued under the following circumstances:

- Adverse events for which continued exposure to the study drug would be detrimental
- Abnormal renal laboratory results requiring discontinuation (see [Section 7.4](#))
- Abnormal liver laboratory results requiring discontinuation (see [Appendix 2](#))
- Platelets < 75000/ μ L
- Pregnancy
- If a patient develops a medical condition that requires use of prohibited treatment as per [Section 5.5.8](#), or if patient exhibits a behavior of non-compliance regarding prohibited medications
- Patient received a live virus vaccination during the study
- If a patient experiences an unexpected hypersensitivity reaction of grade 4, as defined by the World Allergy Organization Grading System ([Cox 2010](#)), see [Appendix 3](#)
 - Lower or upper respiratory: Respiratory failure with or without loss of consciousness

- Or cardiovascular: Hypotension with or without loss of consciousness
- Emergency use of epinephrine due to anaphylactic or anaphylactoid reaction
- Any protocol deviation that results in a significant risk to the patient's safety

Patients who discontinue study treatment should NOT be considered withdrawn from the study. They will be expected to perform the Visit 313 (PSW) assessments four weeks after their last dose (except receiving study drug as a part of visit 313) and will be expected to perform all follow-up assessments (Visit 401-405). If they fail to return for these assessments for unknown reasons, every effort (e.g., telephone, e-mail, letter) should be made to contact them.

The investigator must provide follow-up medical care for all patients who are prematurely withdrawn from the study, or must refer them for appropriate ongoing care. This care may include initiating another treatment outside of the study as deemed appropriate by the investigator

The investigator must also contact the IRT to register the patient's discontinuation from study treatment.

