2.4 Treatments (study treatment, rescue medication, concomitant therapies, compliance)

2.4.1 Study treatment / compliance

Patients will receive two subcutaneous injections every 4 weeks at 13 visits during the open label treatment epoch (i.e. at Day 1, Week 4, Week 8, Week 12 to Week 48).

Compliance is assured as study drug needs to be administered by study personnel every 4 weeks via subcutaneous injection. Administration of study drug, date, time and injection site will be recorded in the source documents and on the Drug Administration Record eCRF for each injection.

The analysis of study treatment data will be based on the Safety set.

The duration of exposure to study treatment in weeks will be summarized by Safety set. Duration of exposure is defined as the date of the last treatment minus the date of first extension study drug administration plus 4 weeks (28 days).

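### SAP 2.1.5 and 2.4.1 define duration of exposure inconsistently, and neither handles a patient's death correctly

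*SAP*

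**What the plan says.** Duration of exposure is defined in two places in the SAP.

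- **SAP 2.1.5** gives a general rule: "The subject's exposure will be calculated using last dose + 28 days". It then repeats the rule for one group, "If a subject discontinued early during the treatment period, then exposure will be calculated using last dose + 28 days", and attaches an exception to that group only: "unless the patient dies, in which case the date of death will be used". Nothing limits the exception to deaths within 28 days of the last dose or to deaths in the treatment epoch.
- **SAP 2.4.1**, which plans the exposure summary, defines duration as "the date of the last treatment minus the date of first extension study drug administration plus 4 weeks (28 days"). It does not mention death.

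Three other parts of the plan bear on this:

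- Protocol 5.6.2 keeps early discontinuers under observation: "Patients who discontinue study treatment should NOT be considered withdrawn from the study". They have a visit four weeks after their last dose (the PSW visit) and then "will be expected to perform all follow-up assessments (Visit 401-405").
- Protocol 3.1 makes that follow-up 48 weeks long, without study drug.
- SAP 2.5.1.3 reports deaths on study without restricting them to the treatment epoch.

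Protocol 9.3 asks only for a summary of time exposed. The legible part of SAP section 4 does not reconcile the two definitions.

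**The concern.** For an early discontinuer who dies, the two rules agree only if death falls exactly 28 days after the last dose. If death comes later, 2.1.5 as worded treats drug-free follow-up as time on drug. If it comes sooner, 2.4.1 credits exposure after the patient has died. Two programmers working from different sections would produce different tables, and neither would be right for every patient.

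The 2.1.5 exception also divides patients in a way that has no evident purpose. A treatment completer who dies in follow-up stays at last dose plus 28 days, while an early discontinuer who dies on the same study day is extended to the date of death. A patient who dies shortly after dose 13 has missed no dose, so on the natural reading the exception does not apply and days after death are counted under both sections.

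What is at stake is the accuracy of the exposure summary for the few patients who die, and of its maximum. SAP Table 1-4 repeats the summary for the Japanese subgroup.

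**Working it through.** **Inputs.** First extension dose is Day 1. Dosing runs "at Day 1, Week 4, Week 8, Week 12 to Week 48" (SAP 2.4.1), so dose 13 is on Day 337 (Protocol Table 6-1). Follow-up lasts 48 weeks, or 336 days (Protocol 3.1). Expected enrolment is about 240 (Protocol 9.7). SAP 2.1.5 names no start date, so I take the first extension dose and count without an extra day, as 2.4.1 does.

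**Formulas.**

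- 2.4.1: last dose − first dose + 28.
- 2.1.5, early discontinuer who dies, read literally: date of death − first dose.
- Difference (2.1.5 minus 2.4.1): date of death − (last dose + 28).

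**The plan's own figure.** A full course under 2.4.1 is 337 − 1 + 28 = 364 days, and 364/7 = 52.0 weeks. This matches the planned 52 weeks in Protocol 5.2.

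**Example.** A patient stops after the third dose, on Day 57. The PSW visit falls on Day 57 + 28 = Day 85. If follow-up runs 48 weeks from there, it ends on Day 85 + 336 = Day 421. SAP 2.4.1 gives 57 − 1 + 28 = 84 days (12.0 weeks) whenever the patient dies.

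| Day of death | 2.1.5, literal (days) | 2.4.1 (days) | Difference | Earlier of the two end dates (days) |
|---|---|---|---|---|
| 71 (14 days after last dose) | 70 | 84 | −14 | 70 |
| 85 | 84 | 84 | 0 | 84 |
| 169 | 168 | 84 | +84 | 84 |
| 253 | 252 | 84 | +168 | 84 |
| 337 | 336 | 84 | +252 | 84 |
| 400 | 399 (57.0 weeks) | 84 | +315 | 84 |
| 421 | 420 (60.0 weeks) | 84 | +336 | 84 |

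The ceiling of 336 days does not depend on when the last dose was given. For a death on Day 400, this three-dose patient would be shown with 399 days, while a patient who had all 13 doses on schedule and died on the same day would be shown with 364.

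**Death soon after dose 13.** Take a death on Day 351, 14 days after the dose. The patient lived 351 − 1 = 350 days from first dose, but 2.4.1 and the general rule in 2.1.5 both give 364. The excess is 14 days, and it cannot be more than 28.

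**Effect on the mean.** The Day 400 death shifts mean exposure by 315/240 = 1.3 days. At the ceiling, 336/240 = 1.4 days, or 336/(240 × 364) = 0.38% of full-course patient-days. The documents give no count of such deaths; if there were 1 to 3, each at the ceiling, the shift would be 1.4 to 4.2 days.

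**Sensitivity to the follow-up calendar.** If early discontinuers instead kept the calendar schedule to Day 701, the largest difference in the example would be 701 − 1 − 84 = 616 days. Protocol 5.6.2 ties the PSW visit to the last dose, so I do not use this as the base case.

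**The case against.** The best defence is that the 2.1.5 clause was meant to shorten exposure, not extend it. It opens with a subject who stops during the treatment period and never mentions follow-up, so its author probably had in mind a patient who dies before the 28 days run out. Moreover, 2.4.1 is the section that plans the table, and its formula can never exceed last dose plus 28 days. A reader might infer from 2.1.5 that early discontinuers who die will be reported with months of false exposure. The documents do not establish that: it happens only if 2.1.5 is programmed literally in preference to 2.4.1. What remains is that the SAP states two rules, does not say which governs, and does not put the likely intention into words.

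A reader might also infer that the safety results rest on this variable. They do not. SAP 2.5.1 reports adverse events as numbers and percentages of patients and defines treatment emergence by 16 weeks from last dose, and no exposure-adjusted rate appears in the legible text. Nor does that text plan a total exposure for patients who died or a listing of derived exposure, so errors in such outputs cannot be claimed. Dosing dates are recorded on the eCRF and deaths are listed, so the true dosing history stays recoverable.

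Last minus first dose plus one dosing interval is a common convention, and its error at death is at most 28 days. That is fair as to size, but it is no reason to count days after death when 2.1.5 already tries to avoid doing so. One could also argue, since Protocol 5.6.1 ties treatment completion to the full 52 weeks, that a death just after dose 13 is an early discontinuation. The SAP does not say so, and the same 28-day ceiling applies.

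**Conclusion.** The inconsistency is real and minor. As worded, 2.1.5 can overstate exposure for an early discontinuer who dies in follow-up, by up to about 336 days on the assumption that follow-up runs 48 weeks from the PSW visit. SAP 2.4.1 can overstate it by up to 28 days for any patient who dies soon after a dose. The harm is limited to individual values and the maximum in the duration-of-exposure summary; the mean moves by about 1 day per such patient in 240. All of this depends on such a death occurring and, for the larger figure, on 2.1.5 being the rule that is programmed. The planned adverse event percentages are unaffected.

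**What to change.** Use one definition in SAP 2.1.5 and 2.4.1, for completers and early discontinuers alike:

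- End of exposure = the earlier of last dose + 28 days and date of death.
- Duration of exposure = end of exposure − date of first extension dose.

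This keeps a full course at 364 days (52.0 weeks), gives 84 days for the Day 57 example whenever death occurs in follow-up, and stops the count at death when a patient dies within 28 days of a dose. The simplest edit is to state the rule once in 2.1.5 and have 2.4.1 refer to it. The cost is a change of SAP wording and about one line of programming; it needs no new data and no change to study conduct.
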